3.1.2 Exclusion Criteria

- Contraindications according to the SPC
- Patients who are actually followed in the ReAlise registry (M03-634)

3.2 Safety and Efficacy Variables / Schedule of Assessments

This is a long-term observational study with the objective of documenting safety and efficacy of HUMIRA® (adalimumab) in normal rheumatological clinical practice.

3.2.1 Safety Variables

The physician will be asked to document the adverse events on Adverse Events DRFs (see Section 4.0 “Adverse Events/Adverse Event Reporting”).

For all serious adverse events (SAEs) reports should be sent by fax to Abbott (for contact information and fax number see Section 4.4 “Adverse Event Reporting”).

Special attention for documentation and follow-up is recommended when one of the following adverse events occur:

- malignancy, including lymphoma
- serious infection, including sepsis, tuberculosis and other opportunistic infections
- lupus-like syndrome
- demyelinating disease
- aplastic anaemia and other severe bone marrow suppressions
- congestive heart failure

In case of pregnancy a pregnancy report form (Appendix E) should be faxed to Abbott using the fax number used for SAE forms (Section 4.4)

3.2.2 Efficacy Variables

Data on the following individual parameters will be collected if assessed as part of clinical practice at each site:

- 28 joint assessment

- physical function (HAQ)
- inflammatory parameter (ESR, CRP)
- concomitant medication
- change in concomitant steroids, NSAIDs
- assessment of non-medical complications (number of non-working days, number of days of hospitalization, ...)
 - for patients with polyarticular or oligoarticular erosive psoriatic arthritis:
 - % of the Body Surface Area (BSA) with psoriatic skin lesions
 - for patients with oligoarticular erosive psoriatic arthritis:
 - Numerical Rating Scale (score of 0 to 10) for the disease activity in the most important joint by the patient (0 = no disease activity during the previous days, 10 = maximal activity during the previous days)
 - Numerical Rating Scale (score of 0 to 10) for the disease activity in the most important joint by the physician (0 = no disease activity during the previous days, 10 = maximal activity during the previous days)
 - For patients with Ankylosing spondylitis the BASDAI will be measured

Table 1: Schedule of Study Assessments

Procedure	Day 1	Month* 3, 6, 9, 12, 18, 24, 30, 36, 42, 48, 54, 60
Informed Consent	✓	
Demographics	✓	
Safety Data Collection	✓	✓
Efficacy Data Collection	✓	✓
Concomitant DMARDs, steroids, NSAIDs	✓	
Changes in concomitant DMARDs, steroids, NSAIDs		✓
Data Report Form Completion	✓	✓

* Data collection at regular visits which are closest to time points described

3.3 Study Procedures

The following procedures will be performed during the study at the time points specified in Table 1, Schedule of Assessments.

3.3.1 Independent Committee Approval

Should the institution/affiliation, and/or national regulation, require an independent committee approval/notification of this protocol, (and related informed consent), then it shall be the investigator's responsibility to secure such approval prior to further initiating any study procedures.

3.3.2 Informed Consent

All subjects will provide their consent to releasing their information to Abbott Laboratories (sponsor) on an informed consent form, that is signed and dated by the subject prior to the release of any such information to the sponsor. Before informed consent is obtained, the investigator or designee will explain to the subject or the subject's legally acceptable representative, the nature and purpose of the study and the data to be provided to the sponsor. After the informed consent form is signed, the original informed consent form will be placed in the subject's medical record and a signed copy should be given to the subject. A patient informed consent template is provided in Appendices A (french version) and B (dutch version).

3.3.3 Demographics

The physician will determine the patient demographic information at the baseline visit and record it in the Baseline DRF. The demographic information will include date of birth (year of birth if restricted by national regulations) and gender.

3.3.4 Patient History

The physician will determine the patient's current status at the Baseline visit and record it in the Baseline DRF. The patient's status will also note concomitant conditions and whether or not these conditions are currently treated. Changes in concomitant medications being taken to treat RA should also be recorded.

3.3.5 Treatment Modality

The treatment modality will include thorough information on all treatments prescribed by the physician and received by the patient. Since this is an observational study, the subject will be treated in accordance with the investigator's usual and customary medical practice. Abbott Laboratories will not provide any medication or therapy for this study.

3.3.6 Primary Data Collection

The following safety information will be collected: adverse events and serious adverse events. The description of event, start and end date, severity, outcome, causal relationship, and action taken will be recorded.

Data to allow determination of patient's disease activity will be collected. These are 28 joint count of swelling and tenderness (SJC, TJC), physician's global assessment of disease activity, HAQ, ESR and CRP. These data, if available as a result of usual medical practice, will be collected via the DRFs.

Other Data

Changes in concomitant DMARDs, steroids, and NSAIDs as well as the administration schedule of HUMIRA® (adalimumab) should be documented in the DRFs.

3.3.7 Data Report Form (DRF) Completion and Collection

All data associated with this study will be collected and reported via DRFs on 2-part NCR paper or electronically via the web address and password which will be provided. If using paper DRFs the top copy of the form should be forwarded to the data coordination center, the second copy of the form should be retained at site.

At the baseline visit, the investigator should complete the Baseline Data Report Forms by collecting and reporting on the forms all available required information, including visit date, demographic data, concomitant diseases and medication, etc. If using paper DRFs the enrolment fax should be completed and faxed immediately to the data coordination center.

At subsequent visits corresponding to the schedule of assessments (Table 1), the investigator should complete the appropriate DRF by collecting and reporting on the forms all available information. Since this is an observational study, data from the patient visit following normal clinical practice, which most closely corresponds to the recommended schedule of assessment at Month 3, Month 6, Month 9, Month 12, Month 18, Month 24, Month 30, Month 36, Month 42, Month 48, Month 54, and Month 60 will be accepted.

If the subject is withdrawn from the study at any time or completes the 5-year observation period an Early Termination DRF should be completed.

3.4 Withdrawal of Subjects from Study

A subject may withdraw from the study at any time without prejudice. The investigator may discontinue any subject's participation for any reason. If a patient withdraws or is withdrawn from the study, such should be noted, along with the reason for withdrawal, on the Early Termination DRF.

3.5 Study Management

Abbott SA/NV will manage the study, collect all study information via DRFs, and complete all statistical analysis of the study, or will contract out parts to a Contract Research Organisation (CRO).

4

ADVERSE EVENTS / ADVERSE EVENT REPORTING

The investigator will monitor each subject for clinical and laboratory evidence of adverse events on a routine basis throughout the study. The investigator will assess and record any adverse event in detail on the adverse event DRF including the date and time of onset, description, severity, time course, duration and outcome, relationship of the adverse event to study drug, an alternate etiology for events not considered "probably related" to study drug, final diagnosis/syndrome (if known) and any action(s) taken. For adverse events to be considered sporadic, the events must be of similar nature and severity. Adverse events, whether in response to a query, observed by study-site personnel, or reported spontaneously by the subject, will be recorded.

All adverse events will be followed to a satisfactory conclusion.

4.1

Definitions

4.1.1

Adverse Event

An **adverse event** is defined as any untoward medical occurrence in a subject or clinical investigation subject administered a pharmaceutical product and which does not necessarily have a causal relationship with this treatment. An adverse event can therefore be any unfavorable and unintended sign (including an abnormal laboratory finding), symptom, or disease temporally associated with the use of a medicinal product, whether or not the event is considered causally related to the use of the product.

Such an event can result from use of the drug as stipulated in the protocol or labeling, as well as from accidental or intentional overdose, drug abuse, or drug withdrawal. Any worsening of a pre-existing condition or illness (except RA) is considered an adverse event. Laboratory abnormalities and changes in vital signs are considered to be adverse events only if they result in permanent or temporary discontinuation of treatment with HUMIRA® (adalimumab), necessitate therapeutic medical intervention and/or if the investigator considers them to be adverse events.

An elective surgery/procedure scheduled to occur during a study will not be considered an adverse event. However, if a pre-existing condition (except RA) deteriorates unexpectedly during the trial (e.g., surgery performed earlier than planned), then the deterioration of the condition for which the elective surgery/procedure is being done will be considered an adverse event.

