3.1 Study Population

Patients with rheumatoid arthritis, psoriatic arthritis or ankylosing spondylitis who have been prescribed HUMIRA® (adalimumab) within local reimbursement guidelines for anti-TNF α 's may be enrolled in the study.

HUMIRA® (adalimumab) is used in a normal clinical setting according to label.

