5 DETERMINATION OF SAMPLE SIZE

Since the purpose of this study is to assess the long-term treatment safety, and efficacy of patients treated with HUMIRA® (adalimumab), as many of these patients as are willing to participate in this follow-up will be enrolled. As it is an observational study, no inferential statistical techniques will be applied to data.

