5.1.2 Planned Methods of Statistical Analysis

Demographics and Baseline Characteristics

Demographic and baseline variables will be described by summary statistics. For continuous data, n, mean, standard deviation, minimum, 1st quartile, median, 3rd quartile, and maximum will be presented. For categorical data, absolute and relative frequency will be calculated.

Safety Analyses

Adverse events will be analysed by presenting frequency and percentage. Furthermore, adverse events of special interest, e.g. serious adverse events, or adverse events leading to discontinuation of treatment with HUMIRA® (adalimumab), will be listed.

Efficacy Analysis

The efficacy analysis of continuous variables (e.g. joint count) will be done descriptively by presenting summary statistics and confidence intervals.

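### Only worsening of RA is exempt from the adverse event definition, so AE totals may not be comparable between RA and PsA/AS

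*Protocol*

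**What the plan says.** Protocol 4.1.1 sets the rule: "Any worsening of a pre-existing condition or illness (except RA) is considered an adverse event". Its paragraph on elective procedures carries the same exemption: the deterioration is an AE "if a pre-existing condition (except RA) deteriorates unexpectedly during the trial". Protocol 3.1 opens the study to three diseases: "Patients with rheumatoid arthritis, psoriatic arthritis or ankylosing spondylitis who have been prescribed" adalimumab. No section exempts worsening of PsA or AS.

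The general definition at the start of Protocol 4.1.1 is wider. It covers "any unfavorable and unintended sign (including an abnormal laboratory finding), symptom, or disease temporally associated with the use of a medicinal product" and exempts no disease.

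A serious AE is an AE that meets a seriousness criterion (Protocol 4.1.2; SAP 1.5), so it inherits the AE definition. SAP 2 reports AEs for each indication and for all patients together. The SAP's AE rules deal with missing onset dates, multiple MedDRA coding, year windows and denominators; none deals with worsening of the treated disease. SAP 1.4 leaves the description of data-handling rules to the statistical report, which is not among the documents.

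**The concern.** The same clinical event can be counted differently according to diagnosis. A flare of AS that leads to hospital admission is a serious AE under the worsening rule; a flare of RA with the same consequence is not captured by that rule. Likewise, a PsA or AS patient who stops treatment because the disease worsened can enter the count of AEs causing discontinuation, while the RA counterpart may not.

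The AE tables are the safety result of a descriptive study, and the RA, PsA and AS tables have the same layout. A reader who sets them side by side could take a difference in definition for a difference in safety. The All Patients totals could combine two definitions without saying so.

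**Working it through.** **1. Reproduce the plan's total.** Inputs are the counts in SAP 1.2: RA 2,836; PsA 1,127; AS 1,957.

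- 2,836 + 1,127 + 1,957 = 5,920, the stated total.

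**2. Patients under each reading of the rule.**

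- Worsening of the treated disease counts: 1,127 + 1,957 = 3,084; 3,084 / 5,920 = 52.1%.
- Exempt under that rule: 2,836 / 5,920 = 47.9%.
- Within the 3,084: AS 1,957 / 3,084 = 63.5%; PsA 1,127 / 3,084 = 36.5%. Whether psoriatic skin worsening belongs to the treated disease matters only for the PsA patients. Protocol 3.2.2 collects the percentage "of the Body Surface Area (BSA) with psoriatic skin lesions" as an efficacy variable in them.

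**3. Tables touched.** The headline tables are 3.1.1, 3.2.1, 3.3.1, 3.4.1 and 3.5.1, in four sections (RA, PsA, AS, All Patients): 5 × 4 = 20, of which 15 are by indication and 5 pooled.

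**4. What the planned tables already allow.** Preferred-term tables number 7 per section (3.1.3, 3.2.3, 3.3.3, 3.4.3, 3.5.3, 3.7.1, 3.7.2), so 7 × 4 = 28, plus 3.8.1 for All Patients = 29.

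- *Event counts and rates, all AEs:* 3.4.3 and 3.5.3 give events by term. Chosen terms can be subtracted.
- *Overall serious AE counts:* 3.7.2 allows the same. No serious AE table by term is listed by year or cumulative period, so serious AE counts and rates by period cannot be adjusted.
- *Patient counts:* a patient can have several terms, so subtraction fails. Let A be patients with any AE (3.1.1), t the patient counts of the worsening terms and u those of the other terms (3.1.3). Patients with at least one other AE lie between max(A − Σt, largest u) and min(A, Σu). That is a bound, not the count.
- *AEs causing discontinuation:* none of the 29 tables breaks these down by term. Protocol 5.1.2 says that "adverse events leading to discontinuation of treatment with HUMIRA® (adalimumab), will be listed", which identifies the events but gives no adjusted total.

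**5. What cannot be computed.** Let b be the rate of other AEs, w the recorded rate of treated-disease worsening in PsA/AS, and v the same in RA. The totals compared are b + w and b + v. The documents give none of the three, so no effect on a rate or rate ratio can be derived.

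**The case against.** The strongest reply is that the RA wording is left over from before the other indications were added and that everyone read it as the treated disease. There is support for this. Protocol 3.3.4, which applies to all patients, says "Changes in concomitant medications being taken to treat RA should also be recorded". Protocol 5.1.1 suggests subgroups by use of RA medications. The Introduction describes AS as being added by amendment. If sites read it so, w is close to zero and the asymmetry disappears. This stands as a possibility, but the documents cannot show what sites did.

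Second, a reader might infer that RA flares are absent from the data. The documents do not support that: the general definition in 4.1.1 has no exemption, so some RA flares may have been recorded.

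Third, a reader might infer that the analysis itself had no harmonising rule. That also goes too far. The absence is certain for the SAP only, because SAP 1.4 points to a report that is not supplied.

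Fourth, nothing formal rests on the comparison. The protocol says "no inferential statistical techniques will be applied to data"; the SAP's only tests compare baseline data of completers and non-completers; and comparing AE totals between indications is not a stated objective. The events singled out for attention in Protocol 3.2.1, such as malignancy, serious infection and demyelinating disease, are not worsening of RA, PsA or AS. All of this stands and limits the weight of the point. It leaves the conflict in wording, and totals that the SAP will print by indication and pooled.

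**Conclusion.** The point holds as a minor matter of reporting and comparability. The RA-only exemption, the enrolment of three indications and the lack of a harmonising rule in the SAP are certain. Read literally, the rule splits the analysed patients 52.1% to 47.9%, so neither reading is confined to a small group.

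The consequence is not certain. It assumes that sites applied the exemption as written and recorded PsA and AS worsening as AEs more readily than RA worsening. A reader might conclude that the AE results by indication are biased, or that PsA and AS will look less safe than RA. The documents support neither conclusion: they contain no AE or flare counts and nothing on site practice. Confidence is high for the wording only, not for the size of any effect.

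**What to change.** 1. Keep all planned AE tables in full as the main results.
2. Add to the SAP a sensitivity analysis that excludes worsening of each patient's own treated disease. Use a medically reviewed list of preferred terms applied by indication: RA terms only in RA patients, PsA terms only in PsA patients, AS terms only in AS patients. A single list applied to everyone would wrongly remove, for example, a psoriasis term in an RA or AS patient. Use the recorded event description and final diagnosis (Protocol 4) as support where they are in the database.
3. State whether psoriatic skin worsening counts in PsA, and that the list was set after data receipt (SAP 1.2).
4. Limit it to what subtraction cannot recover: patient-level totals (3.1.1, 3.2.1, 3.3.1), AEs causing discontinuation, and serious AE counts and rates by period. Give these for RA, PsA, AS and All Patients, with the excluded events on a separate line.
5. Add a footnote and a limitation: 4.1.1 exempted only RA worsening, unrecorded RA flares cannot be restored, and site practice is unknown.
6. Note that the RA-only wording and the three enrolled indications must be reconciled. This does not change data already collected.

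**Cost.** If each measure is one row, the 12 patient-level tables gain at most 4 measures × 2 rows × 12 = 96 rows. Tables 3.4.1 and 3.5.1 gain at most 2 measures × 2 rows × 8 tables = 32, so 128 in all, from the same program with a filter. Medical sign-off of the list is also needed.

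**Downsides.** The list is not blind to the data, and non-specific joint or back symptoms cannot be separated cleanly from disease worsening. If the two versions prove nearly the same, that is itself worth reporting.

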4.1.2 Serious Adverse Event

If an adverse event meets any of the following criteria, it is to be reported to Abbott as a serious adverse event within 24 hours of occurrence or notification of the study site:

Death of Subject	An event that results in the death of a subject.
Life-Threatening	An event that, in the opinion of the investigator, would have resulted in immediate fatality if medical intervention had not been taken. This does not include an event that would have been fatal if it had occurred in a more severe form.
Hospitalization	An event that results in an admission to the hospital for any length of time. This does not include an emergency room visit or admission to an outpatient facility.
Prolongation of Hospitalization	An event that occurs while the study subject is hospitalized and prolongs the subject's hospital stay.
Congenital Anomaly	An anomaly detected at or after birth, or any anomaly that results in fetal loss.
Persistent or Significant Disability/Incapacity	An event that results in a condition that substantially interferes with the activities of daily living of a study subject. Disability is not intended to include experiences of relatively minor medical significance such as headache, nausea, vomiting, diarrhea, influenza, and accidental trauma (e.g., sprained ankle).

Important Medical Event Requiring Medical or Surgical Intervention to Prevent Serious Outcome	An important medical event that may not be immediately life-threatening or result in death or hospitalization, but based on medical judgment may jeopardize the subject and may require medical or surgical intervention to prevent any of the outcomes listed above (i.e. , death of subject, life-threatening, hospitalization, prolongation of hospitalization, congenital anomaly, or persistent or significant disability/incapacity). Examples of such events include allergic bronchospasm requiring intensive treatment in an emergency room or at home, blood dyscrasias or convulsions that do not result in inpatient hospitalization, or the development of drug dependency or drug abuse.
Spontaneous Abortion	Miscarriage experienced by study subject.
Elective Abortion	Elective abortion performed on study subject.

4.2 Adverse Event Severity

The investigator will use the following definitions to rate the severity of each adverse event:

Mild	The adverse event is transient and easily tolerated by the subject.
Moderate	The adverse event causes the subject discomfort and interrupts the subject's usual activities.
Severe	The adverse event causes considerable interference with the subject's usual activities and may be incapacitating or life-threatening.

4.3 Relationship to Study Drug

The investigator will use the following definitions to assess the relationship of the adverse event to the use of study drug:

Probably Related	An adverse event has a strong temporal relationship to study drug or recurs on re-challenge and another etiology is unlikely or significantly less likely.
-------------------------	--

Possibly Related	An adverse event has a strong temporal relationship to the study drug and an alternative etiology is equally or less likely compared to the potential relationship to study drug.
Probably Not Related	An adverse event has little or no temporal relationship to the study drug and/or a more likely alternative etiology exists.
Not Related	An adverse event is due to an underlying or concurrent illness or effect of another drug and is not related to the study drug (e.g., has no temporal relationship to study drug or has a much more likely alternative etiology).

4.4 Adverse Event Reporting

In the event of a serious adverse event, whether related to HUMIRA® (adalimumab) or not, the investigator will notify one of the following person by faxing the appropriate adverse event form within 24 hours of being made aware of the serious adverse event.

5 DETERMINATION OF SAMPLE SIZE

Since the purpose of this study is to assess the long-term treatment safety, and efficacy of patients treated with HUMIRA® (adalimumab), as many of these patients as are willing to participate in this follow-up will be enrolled. As it is an observational study, no inferential statistical techniques will be applied to data.

